#### 7.9 Interim analysis

No interim analysis was conducted.

#### 7.10 Further issues

Due to the exploratory character of the study, modifications and extensions of the prespecified analyses are possible without constraints, if indicated by the data.

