#### 2.3 Procedures prior to statistical analysis

After completion of check of all available study data, the database will be closed. Data Management ensures that no data modifications are possible by Biostatistics within this database. Thereafter, only the responsible data manager and the project statistician will be privileged to have access to the database. Any changes to the analyses after the SAP has been finalized will be clearly described in the study report.

After database closure the data will be transferred electronically to the statistical software package SAS® data set format for statistical analysis. The SAS® data sets will be considered as source data sets for statistical analysis.

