#### 2.5 Quality control

The SAP is consistent with the underlying study protocol. If there is a need for deviating substantially from the protocol-defined analysis, this is described in detail. The methods described in this SAP are mandatory for statistical programming.

Quality control (QC) of statistical programming will be performed according to the QC plan, which specifies all planned actions to ensure that the performed analyses are correct, traceable and in line with the planned analysis as specified in the SAP. The QC plan also includes filing of statistical programs, outputs and documentation of QC. It is finalized by the project statistical programmer before the start of any programming activities.

Documentation of QC is filed in the trial master file.

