## 7 Statistical methodology

## 7.1 General methodology

All statistical analyses will be carried out by means of the SAS® package (version 9.4).

Quantitative data (e.g. age) will be described by the statistical parameters valid N, missing N, mean, standard deviation (SD), minimum, the 25%-quartile, median, the 75%-quartile, and the maximum.

Qualitative data (e.g. gender) will be presented by means of (absolute and relative) frequency distributions. If applicable, two methods will be followed for calculation of percentages. The first method considers missing data as a separate group, which results in the same sample size for all parameters. The second method of calculation is based on the valid data per parameter, excluding patients with missing values ("valid data analysis"). Accordingly, this results in different sample sizes. In general, description of results within the report refers to the "valid data analysis".

For categorical variables associated with score values, the mean will be calculated as well.

Two-sided 95% confidence intervals will be provided for the primary, and if applicable, the secondary variables defined by proportions.

Statistical methods which differ from the above mentioned methods or require further description will be addressed in the following sections.

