## 7.5 Primary variable

The primary variable will be evaluated for FAS.

For the time period between 12 months after LCIG initiation and the visit, appropriate time points will be used.

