#### 7.8 Regression analyses

For the application of regression analysis, missing/unknown data for prognostic factors are imputed. Imputation is planned to be accomplished by a regression based single imputation method where missing values of one predictor variable are predicted by regression models with a set of remaining potential prognostic variables as independent variables. This might require adequate preprocessing of the data. Modification of this imputation strategy is possible if implied by the data.

Regression analyses will be evaluated for FAS and conducted on imputed data.

Regression analyses will be performed separately for each of the two primary variables (see Section 6.4):

LCIG monotherapy 1 (LCIG monotherapy 2, respectively) at 12 months after LCIG initiation will be used as dependent (i.e. response) variable in two multivariable logistic regression models. The independent variables (i.e. potential predictors) will be checked for collinearity.

For the first multivariable logistic regression model the following variables will be considered as potential predictors (i.e. independent variables):

Table 7-2: Potential predictors used for regression analysis 1

Variable	Range	Dichotomization/Grouping
Age	numeric	-
Gender	Male, Female	Male vs. Female
Race	White, Black, Asian, Mixed, Other	White vs. Non-White
Education	No formal education, primary school, secondary school, non-university professional education, university	Less than secondary school vs. secondary school or higher
Total number of symptoms	numeric	
Number of symptoms related to treatment	numeric	
Number of motor symptoms	numeric	-
Number of non-motor symptoms	numeric	-
Total daily LEDD at LCIG initiation	numeric	-
Time from PD diagnosis to start of LCIG	numeric	-
Duration of 'Off' state time during a 24h period	numeric	-
Duration of dyskinesia during a 24h period	numeric	-
UPDRS V prior to LCIG initiation (if available)	numeric	-
Any device aided therapy other than LCIG in the past	Yes, No	Yes vs. No
Any dopamine agonists in the past	Yes, No	Yes vs. No
PD motor phenotype	Tremoric, Akinetic rigid, Mix	
Time from PD diagnosis to motor fluctuation	numeric	
Time from PD diagnosis to onset of morning akinesia	numeric	
Country		
GNI	numeric	

Categorical predictors will be dichotomized / grouped as shown in Table 7-2 in order to simplify interpretation.

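### SAP 7.10 lets any planned analysis, the primary variables included, be changed without limit on the basis of the data, and nothing requires the planned primary result to be shown or to stay primary

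*SAP*

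**What the plan says.** SAP 7.10 gives as its reason "Due to the exploratory character of the study" and then states that "modifications and extensions of the prespecified analyses are possible without constraints, if indicated by the data". It covers modification as well as addition, names no exempt analysis, and takes the data as its trigger.

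Two other places leave narrower choices open:
- SAP 7.8, on imputing missing predictors: "Modification of this imputation strategy is possible if implied by the data".
- SAP 7.5, in the primary-variable section: "For the time period between 12 months after LCIG initiation and the visit, appropriate time points will be used". These points are not listed.

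Three provisions pull the other way:
- SAP 2.5: "The methods described in this SAP are mandatory for statistical programming".
- SAP 2.5, on departures from the protocol: "If there is a need for deviating substantially from the protocol-defined analysis, this is described in detail".
- SAP 2.3: "Any changes to the analyses after the SAP has been finalized will be clearly described in the study report".

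On the primary result, SAP 7.1 says: "Two-sided 95% confidence intervals will be provided for the primary, and if applicable, the secondary variables defined by proportions". Protocol 9.5 sizes the study on the width of that interval, with at least 385 evaluable patients and about 400 to be included.

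**The concern.** A programmer cannot be bound by mandatory methods and also be free to change them without limit, so SAP 2.5 and 7.10 cannot both be followed as written. The disclosure duty in SAP 2.3 does not settle the matter. A report could describe a change, present only the changed primary percentage, and comply with every sentence of the SAP.

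The latitude matters because the headline figure depends on definition. Protocol 9.2.7.7 gives one definition of monotherapy, based on what is taken during infusion hours. SAP 6.4 has two primary variables and does not say which leads. The first is the stricter, so its percentage cannot exceed the second's. The second depends on the recorded reason for the add-on medication. Protocol 9.7 leaves statistical detail to the SAP, so if 7.10 releases the SAP, the detailed derivation is not firmly fixed anywhere. At stake are selective reporting of the primary percentage and the meaning of the interval around it.

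**Working it through.** **1. The plan's own figure.** Protocol 9.5 uses a two-sided 95% interval, an underlying percentage of 50% and a half-width of 5 points:

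n = z² · p(1 − p) / d² = 1.96² × 0.25 / 0.05² = 384.16, rounded up to 385.

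This reproduces the stated 385. The half-width is 4.99 points at 385 and 4.90 points at 400. The standard error (SE) at 400 is √(0.25 / 400) = 2.5 points.

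**2. What happens if a data-chosen version is reported instead.** The documents do not say how many versions might be tried or how alike they would be. I therefore assume K equally valid versions of one proportion, with the same true value, an SE of 2.5 points, normal estimates and a common correlation ρ, and that the highest is reported with its ordinary 95% interval. The figures come from 400,000 simulated draws per cell.

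| K | Result | ρ = 0 | ρ = 0.5 | ρ = 0.8 | ρ = 0.9 |
|---|---|---|---|---|---|
| 2 | Coverage, % | 95.0 | 95.0 | 94.9 | 95.0 |
| 2 | Upward shift, points | 1.42 | 1.00 | 0.63 | 0.45 |
| 3 | Coverage, % | 92.7 | 93.6 | 94.4 | 94.6 |
| 3 | Upward shift, points | 2.12 | 1.49 | 0.95 | 0.67 |
| 5 | Coverage, % | 88.1 | 90.8 | 93.2 | 94.2 |
| 5 | Upward shift, points | 2.91 | 2.06 | 1.30 | 0.92 |

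The K = 5 shifts, divided by 2.5, are 1.16, 0.82, 0.52 and 0.37 SE.

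Two checks by formula:
- K = 5, ρ = 0: 0.975⁵ − 0.025⁵ = 0.881, as simulated.
- K = 2, any ρ: P(max < c) − P(max < −c) = 2Φ(c) − 1, which is 0.95 at c = 1.96. Coverage is therefore exactly 95% for two versions, and the 94.9 in the table is simulation noise. The estimate is still shifted upward.

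With K = 1, that is, with 7.10 not used, coverage is 95% and there is no shift.

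**3. The 0.05 in SAP 7.8.** This is the level for keeping a variable in backward elimination. Table 7-2 has 20 candidates and Table 7-3 has 11. For independent tests with no true predictor, the chance of at least one nominally significant candidate is 1 − 0.95²⁰ = 0.64 and 1 − 0.95¹¹ = 0.43. Simulated backward elimination (400 patients, 40% outcome rate, independent normal predictors, 600 runs) keeps at least one in 0.61 and 0.42 of data sets. All of this holds without any use of 7.10.

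**4. Whether the regressions can be run exactly as written.** SAP 6.3 defines the total number of symptoms as the sum of the motor, non-motor and treatment-related counts. Table 7-2 lists the total and all three components. The GNI table in 7.8 assigns one value per country, while country is itself a candidate. SAP 7.8 asks for a collinearity check but gives no rule for dropping variables, so some departure from the written list is unavoidable.

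**The case against.** The best defence is that the study is descriptive and sized on precision, with no test attached to the primary endpoint; that SAP 2.3 and 2.5 require changes to be described; and that a SAP clause cannot amend the endpoint, time points and monotherapy definition fixed in the protocol. Much of this stands, and it rules out several stronger readings that a reader might infer:

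- *That 7.10 in itself invalidates the 95% intervals.* It does not. Coverage is at risk only if a data-chosen version is reported in place of the planned one, and even then it stays at 95% for the higher of two versions.
- *That 7.10 breaks a 5% error rate for predictors.* The 0.05 is a retention threshold. The plan attaches no type I error claim to it, and step 3 shows that the selection procedure never had a 5% error rate.
- *That readers could not tell that an analysis had been changed.* SAP 2.3 means they would be told. What they might lack is the planned number.
- *That the primary hypothesis mentioned in the protocol's rationale makes this a confirmatory study.* That sentence has no null value, threshold or test.
- *That SAP 7.5 replaces the primary time points.* It adds points after month 12 and leaves the five planned ones in place.

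It is also fair that versions of one proportion in the same patients would probably be highly correlated, which favours the smaller figures in the table.

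The defence does not supply a sentence that keeps the planned primary result in the report, and it does not reconcile 2.5 with 7.10. A descriptive percentage also needs a fixed definition for its interval to mean what it says.

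**Conclusion.** The concern holds as a point about transparency and selective reporting. SAP 7.10 is a stated permission, not a gap. It covers the primary variables, conflicts with SAP 2.5, and is limited only by a duty to describe changes.

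The numerical consequence is conditional and illustrative. If the highest of five equally valid versions were reported, coverage would be about 88% to 93% for correlations from 0 to 0.8 (94.2% at 0.9). The upward shift would be 0.4 to 1.2 SE for correlations from 0.9 to 0, about 1 to 3 points against a planned precision of ±5. Five versions, the correlations and the choice of the highest are all assumptions. The model covers noise between equally valid versions only. A change of definition could move the percentage by more, and the documents give no basis for a figure.

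**What to change.** Replace SAP 7.10 with:

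> The primary variables at the five planned time points (LCIG initiation and months 3, 6, 9 and 12; sections 6.4 and 7.5) will be derived, analysed and reported as specified, and remain the basis of the primary conclusion. Analyses changed or added after database closure are reported in addition, labelled post hoc, with the reason. The planned regression analyses (7.8) are likewise reported. Where a planned model cannot be fitted, for example because of collinear candidates, the reason is documented and the fallback model is labelled as such.

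Two matching edits follow:
- In 7.8, report any alternative imputation as a sensitivity analysis beside the planned one.
- In 7.5, label results after month 12 as supplementary to the primary variable.

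This costs a few sentences of SAP text. Data collection and sample size are unaffected, and exploratory work remains possible. The small downside is that the planned result must be shown even when a later version is preferred.
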